5.1 Subject informed consent

Prior to performing any study procedures, the Investigator (or designated personnel) will ensure that the subject is given full and adequate oral and written information about the study and the subject must sign the ICF, as described in Section 11.2.1.

There is no washout permitted during the study.

5.2 Description of study phases

5.2.1 Screening (Visit 1)

Screening assessments will be performed from Week -5 to Week -4, inclusive, where eligibility for the study will be assessed. Subjects will be requested to attend the clinic after a 6-hour fasting period (apart from water).

Re-screening will be allowed once in the study for subjects who do not meet the screening criteria with the exception of;

- Inclusion criteria #3
- Exclusion criteria #8
- Exclusion criteria #16

All screening assessments will be performed again – with the exception of transvaginal ultrasound and endometrial biopsy; if baseline transvaginal ultrasound and endometrial biopsy are performed within 3 months of re-screening, repeated assessments will not be required.

Written informed consent will be obtained before any screening procedures are performed. The following assessments will be performed (refer to Table 1 for further details):

- Written informed consent
- Inclusion/exclusion criteria
- Demography
- Medical, drug, smoking, alcohol, and surgical history
- Physical examination (complete; see Section 6.7.1)
- Breast examination
- Height and weight
- 12-lead ECG
- Vital signs (including sitting blood pressure, pulse rate, and tympanic body temperature)
- Routine laboratory evaluations (hematology, biochemistry, coagulation, and urinalysis) Note: Liver function labs may be retested once within the Screening window for subjects who are ineligible due solely to exclusion criteria #9
- Reproductive hormone assessments: E2, LH, and FSH (Note: FSH may be retested once within the Screening window for subjects who are ineligible due solely to inclusion criteria #2)
- Transvaginal ultrasound and endometrial biopsy for subjects with a uterus

- Note: Baseline assessments for transvaginal ultrasound and endometrial biopsy will be performed at any time during the Screening period or the Placebo Run-in period, but at least 7 days prior to randomization.
- Note: Subjects qualifying based on transvaginal ultrasound will proceed to endometrial biopsy (see exclusion criteria #8).
- Note: Subjects with insufficient tissue for diagnosis at baseline endometrial biopsy may be retested once within the time window (see exclusion criteria #16).
- Provide VMS diary and educate subject in its use
- AE and prior/concomitant medication recording

5.2.2 Placebo Run-in (Visit 2)

Subjects determined to be eligible based on Screening data will participate in a 2-week Placebo Run-in period beginning at Week -2. Subjects will be requested to attend the clinic after a 10-hour fasting period (apart from water).

The following assessments will be performed (refer to Table 1 for further details):

- Verify inclusion/exclusion criteria
- Verify demography and medical/drug/smoking/alcohol/surgical history
- Physical examination (routine; see Section 6.7.1)
- Vital signs (including sitting blood pressure, pulse rate, and tympanic body temperature)
- Routine laboratory evaluations (hematology, biochemistry, coagulation, and urinalysis)
- Transvaginal ultrasound and endometrial biopsy for subjects with a uterus
 - Note: Baseline assessments for transvaginal ultrasound and endometrial biopsy will be performed at any time during the Screening period or the Placebo Run-in period, but at least 7 days prior to randomization.
 - Note: Subjects qualifying based on transvaginal ultrasound will proceed to endometrial biopsy (see exclusion criteria #8).
 - Note: Subjects with insufficient tissue for diagnosis at baseline endometrial biopsy may be retested once within the time window (see exclusion criteria #16).
- Review VMS diary (re-educate subject if necessary)
- Questionnaires: ISI, MENQOL, PSQI, SF-36, PHQ-8, and GAD7
- Dispense single-blind placebo
- AE and prior/concomitant medication recording

5.2.3 Double-blind Treatment (Visits 3 through 7)

Subjects who successfully complete Screening and Placebo Run-in periods will return to the clinic for the Randomization visit on Day 1 and participate in the Double-blind Treatment period.

Inclusion and exclusion criteria will be reviewed to confirm eligibility prior to randomization.

Randomized subjects who are withdrawn early from the study should, where possible, complete the procedures scheduled for the EOT (Week 12) visit as soon as possible after withdrawal. Every effort should be made to maintain randomized subjects on study, even in cases where treatment has been discontinued.

5.2.3.1 Randomization (Visit 3)

The following assessments will be performed prior to randomization (refer to Table 1 for further details):

- Verify inclusion/exclusion criteria prior to randomization
- Physical examination (routine; see Section 6.7.1; including weight)
- Breast examination
- 12-lead ECG
- Vital signs (including sitting blood pressure, pulse rate, and tympanic body temperature)
- Routine laboratory evaluations (hematology, biochemistry, coagulation, and urinalysis)
- Reproductive hormone assessments: E2, LH, and FSH
- Review VMS diary (re-educate subject if necessary)
- Questionnaires: ISI, MENQOL, PSQI, SF-36, PHQ-8, and GAD7
- Blood sample for MT-8554 PK
- Perform study medication accountability
- Dispense study medication
- AE and prior/concomitant medication recording
- [REDACTED]

5.2.3.2 Week 2 (Visit 4)

- Physical examination (routine; see Section 6.7.1)
- Vital signs (including sitting blood pressure, pulse rate, and tympanic body temperature)
- Routine laboratory evaluations (hematology, biochemistry, coagulation, and urinalysis)
- Review VMS diary (re-educate subject if necessary)
- Questionnaires: PHQ-8 and GAD7
- Blood sample for MT-8554 PK (record most recent dose date and time)
- Perform study medication accountability
- Dispense new study medication
- AE and prior/concomitant medication recording
- Diary compliance [REDACTED] during Week 3

5.2.3.3 Week 4 (Visit 5)

- Physical examination (routine; see Section 6.7.1)
- Vital signs (including sitting blood pressure, pulse rate, and tympanic body temperature)

- Routine laboratory evaluations (hematology, biochemistry, coagulation, and urinalysis)
- Review VMS diary (re-educate subject if necessary)
- Questionnaires: ISI, MENQOL, PGIC, PSQI, SF-36, PHQ-8, and GAD7
- Blood sample for MT-8554 PK (record most recent dose date and time)
- Perform study medication accountability
- Dispense new study medication
- AE and prior/concomitant medication recording
- Diary compliance [REDACTED] during Weeks 6 and 7

5.2.3.4 Week 8 (Visit 6)

- Physical examination (routine; see Section 6.7.1)
- Vital signs (including sitting blood pressure, pulse rate, and tympanic body temperature)
- Routine laboratory evaluations (hematology, biochemistry, coagulation, and urinalysis)
- Review VMS diary (re-educate subject if necessary)
- Questionnaires: PHQ-8 and GAD7
- Blood sample for MT-8554 PK (record most recent dose date and time)
- Perform study medication accountability
- Dispense new study medication
- AE and concomitant medication recording
- Diary compliance [REDACTED] during Weeks 9, 10 and 11

5.2.3.5 Week 12 or early termination (Visit 7; EOT)

- Physical examination (routine; see Section 6.7.1; including weight)
- Breast examination
- 12-lead ECG
- Vital signs (including sitting blood pressure, pulse rate, and tympanic body temperature)
- Routine laboratory evaluations (hematology, biochemistry, coagulation, and urinalysis)
- Reproductive hormone assessments: E2, LH, and FSH
- Transvaginal ultrasound and endometrial biopsy (for subjects with a uterus)
- VMS diary collection
- Questionnaires: ISI, MENQOL, PGIC, PSQI, SF-36, PHQ-8, and GAD7
- Blood sample for MT-8554 PK (record most recent dose date and time)
- Perform study medication accountability
- AE and prior/concomitant medication recording

Subjects who complete through Week 12 may be enrolled into the OLE study (MT-8554-A02) to receive MT-8554 for a further 52 weeks.

5.2.4 Follow-up (Week 16; Visit 8; EOS)

Subjects who do not enroll into the OLE study (MT-8554-A02) will be telephoned by the Investigator (or designee) 30 days after EOT, for a Follow-up visit. Information on any new AEs, follow-up on existing AEs, and prior/concomitant medication will be recorded.

5.2.5 Post-study access to treatment

MT-8554 will not continue to be available to subjects following completion or termination of the study, in accordance with the study information given to the subjects.

5.2.6 Reminder Phone Calls to Subject

Site will make periodic calls to subjects at a minimum during weeks where no in clinic visits occur, to ensure subject compliance with daily VMS diary completion [REDACTED]. AEs reported during the calls will be documented as applicable.

5.2.7 Unscheduled visits

An unscheduled visit is defined as any visit to the Investigator site outside of the Protocol specified study site visits due to safety reasons or when a repeat test and/or measurement is required (e.g., obvious measurement errors, measuring device failure, confirmation of out-of-range results), where the subject is seen by study personnel.

Additional unscheduled samples for safety assessments may be performed at the discretion of the Investigator, if deemed necessary. All unscheduled visits and assessments performed during the visits will be recorded in the eCRF.

6 STUDY PROCEDURES

Procedures will be performed according to the Schedule of Assessments (Table 1). A priority order will be in effect when more than 1 assessment is required at a particular time point and this will be described in a separate document. Time windows for relevant assessments will also be described in a separate document.

6.1 Informed consent form

The Investigator or designee will fully explain the nature of the study to subjects using the IRB-approved informed consent document. When the subject agrees to participate in the study, the subject must voluntarily sign a consent form prior to the initiation of any study procedures. A copy of the signed and dated informed consent document will be given to the subject. The signed and dated original consent form will be retained by the Investigator. Informed consent will be obtained from all subjects. A subject cannot be entered into the study until he/she has signed and dated the consent form.

The Investigator or designee is responsible for ensuring that the subject understands the risks and benefits of participating in the study, including answering any questions the subject may have throughout the study and sharing any new information in a timely manner that may be relevant to the subject's willingness to continue his/her participation in the study.

6.2 Demography

The following subject characteristics will be recorded at Screening: date of birth, sex, weight, height, and race.

6.3 Medical and surgical history

Medical, drug, smoking, alcohol, and surgical history will be recorded. Medical/surgical history includes any medical condition or surgical history prior to Screening.

6.4 Prior and concomitant medication

Prior medications are defined as any medication taken prior to the double-blind treatment period.

[figure not shown]
Any prior medication, including prescription and over-the-counter medications, taken within 1 month prior to Screening will be recorded on the eCRF. Information recorded will include: name of drug, dose, duration of use, and reason for use.

Concomitant medication is defined as any medication, other than study medication, which is taken during the study, including prescription and over-the-counter medications. All concomitant medications taken while the subject is participating in the study will be recorded.

Concomitant medication will be given only if deemed necessary by the Investigator or the subject's personal physician.

6.4.1 Prohibited medication

Subjects must not participate in any other clinical study involving administration of another investigational study medication from Screening through the final Follow-up visit.

Subjects must not take any prescribed or non-prescribed systemic or topical medication (including herbal or dietary supplements) known to possibly have an effect on VMS or sleep during the study. Such drugs include, but not limited to estrogen, gabapentin, clonidine, progestin, black cohosh, soy, phytoestrogens, sedatives, and hypnotics.

Antidepressants prescribed for the treatment of VMS and paroxetine are prohibited during the study period. Other antidepressants are permitted as long as the doses are stable for 6 months or more prior to Screening and no dose adjustments are anticipated during the study period.

6.4.2 Rescue medication

There is no known antidote to MT-8554. In the case of significant AEs, appropriate medical management will be provided by site staff.

6.5 Efficacy assessments

6.5.1 Subjective vasomotor symptoms

Subjects will be asked to record frequency and severity of VMS in an electronic diary beginning at Randomization (Day 1) and throughout the Double-blind Treatment period. To assess eligibility, subjects will also be asked to complete the diary for 14 days each during the Screening and Placebo Run-in periods. See APPENDIX 1 for an example of the VMS diary.

VMS diaries will be provided by the Sponsor and given to subjects by clinic personnel, with instructions on its use. A paper back-up VMS diary card will be used in case of device malfunction, stolen or lost. See Section 9.1 for further information related to VMS diary data collection and transfer.

Definitions of VMS severity levels (per 2003 draft FDA guidance) are provided in Table 2.

Table 2 VMS Severity Levels

Severity	Definition
Mild	Sensation of heat without sweating
Moderate	Sensation of heat with sweating, able to continue activity
Severe	Sensation of heat with sweating, causing cessation of activity

Abbreviations: VMS=vasomotor symptoms

6.5.2 Subject questionnaires

6.5.2.1 Menopause-Specific Quality of Life⁶

The MENQOL is self-administered and consists of a total of 29 items in a Likert-scale format. Each item assesses the impact of 1 of 4 domains of menopausal symptoms, as experienced over the last month: vasomotor (items 1–3), psychosocial (items 4–10), physical (items 11–26), and sexual (items 27–29). Items pertaining to a specific symptom are rated as present or not present, and if present, how bothersome on a 0 (not bothersome) to 6 (extremely bothersome) scale. Means are computed for each subscale by dividing the sum of the domain's items by the number of items within that domain. Non-endorsement of an item is scored a “1” and endorsement a “2,” plus the number of the particular rating, so that the possible score on any item ranges from 1 to 8. See APPENDIX 2 for an example of the MSQOL.

6.5.2.2 Insomnia Severity Index⁷

The ISI is a self-rated, 7-item questionnaire designed to measure a subject's current perception of symptom severity, distress, and daytime impairment. Items include: the severity of sleep onset and maintenance (middle and early morning awakening) difficulties, satisfaction with current sleep pattern, interference with daily functioning, appearance of impairment attributed to the sleep problem, and the degree of concern caused by insomnia. See APPENDIX 3 for an example of the ISI.

6.5.2.3 Pittsburgh Sleep Quality Index⁸

The PSQI is a self-rated questionnaire which assesses sleep quality and disturbances. Nineteen individual items generate 7 “component” scores: subjective sleep quality, sleep latency, sleep duration, habitual sleep efficiency, sleep disturbances, use of sleeping medication, and daytime dysfunction. Scoring of the answers is based on a 0 to 3 scale, whereby 3 reflects the negative extreme on the Likert Scale. The sum of scores of the 7 component scores yields 1 global score. A global sum of 5 or greater indicates a “poor” sleeper. See APPENDIX 4 for an example of the PSQI.

6.5.2.4 36-Item Short Form Health Survey⁹

The SF-36 is a self-rated questionnaire which assess 8 health concepts: physical functioning, bodily pain, role limitations due to physical health problems, role limitations due to personal or emotional problems, emotional well-being, social functioning, energy/fatigue, and general health perceptions. In addition, it includes a single item that provides an indication of perceived change in health. See APPENDIX 5 for an example of the SF-36.

6.5.2.5 Patient Global Impression of Change¹⁰

The PGIC is used to assess the subject's rating of overall improvement. Subjects rate their perceived change on a 7-point scale from ‘very much improved’ to ‘very much worse’. See APPENDIX 6 for an example of the PGIC.

If necessary, further details will be provided in a separate study reference manual.

6.6 Pharmacokinetic assessments

Blood samples will be collected via cannulation or direct venipuncture in a suitable forearm vein. The actual date and time of each blood sample and the most recent dose date and time will be recorded in the source documents and eCRF.

For each PK assessment, a blood sample of approximately █ mL will be collected to ensure there is sufficient plasma for primary and contingency samples.

Sample handling details will be described fully in a separate document. At agreed time points, samples will be sent frozen (packed in dry ice) by courier from the clinic to the lab. Contingency samples will be shipped separately to the primary samples.

Samples will be analyzed using standard methods.

6.7 Safety assessments

Please refer to Section 8 for details of AE management.

6.7.1 Physical examination

The complete physical examination will consist of a routine assessment of major body systems: abdominal, cardiovascular, general appearance, head, eyes, ears/nose/throat, lymph nodes, musculoskeletal, neck, neurological, dermatological, respiratory and 'other'.

The routine physical examination will consist of a routine assessment of the following body systems: abdominal, cardiovascular, general appearance, respiratory and 'other'.

6.7.2 Breast examination

A breast examination (symmetry of breast shape, contour of breast, appearance of skin, nipple, areola, lymph nodes status, presence and characterization of lesions) will be performed at Screening, Visits 3 and 7. The Investigator or designated study staff will perform a clinical examination and record in the eCRF.

6.7.3 Vital signs

Subjects' vital signs (sitting blood pressure, pulse, and tympanic body temperature) will be taken at each visit. Subjects will undergo an assessment of blood pressure at each visit using a blood pressure recording device with an appropriate cuff size and with the subject in a sitting position. The same arm will be used for all measurements. Pulse rate and tympanic body temperature will also be measured. An infrared ear thermometer will be used to measure tympanic body temperature.

The Investigator will perform an overall evaluation of vital signs for safety purposes and the recording will be reported as 'normal', 'abnormal clinically significant (CS)', or 'abnormal not clinically significant (NCS)'.

Abnormalities of clinical significance will be reported as AEs. Repeat measurements will be performed for abnormal results.

6.7.4 Electrocardiogram

A 12-lead ECG will be performed after the subject has rested for at least 5 minutes in the supine position. The Investigator will perform an overall evaluation of the ECG results for safety purposes and the recording will be reported as 'normal', 'abnormal CS', or 'abnormal NCS'. Abnormalities of clinical significance will be reported as AEs. Repeat measurements will be performed for abnormal results.

6.7.5 Transvaginal ultrasound

For subjects who have a uterus, a transvaginal ultrasound will be performed at baseline during the Screening period or the Placebo Run-in period, but at least 7 days prior to randomization, and Week 12 or early termination to measure endometrial thickness. The scans will be performed locally by qualified personnel and a blinded review will be conducted centrally. The Investigator will read the scan at baseline and judge exclusion criterion #8. Procedures for the handling of these assessments will be described in full in separate documents.

6.7.6 Endometrial biopsy

For subjects who have a uterus, and qualify for the enrollment based on the transvaginal ultrasound (exclusion criteria #8), an endometrial biopsy will be performed at baseline during the Screening period or the Placebo Run-in period, but at least 7 days prior to randomization, and Week 12 or early termination to assess endometrial hyperplasia. The biopsy samples will be processed and assessed by central laboratory. Biopsy results will be adjudicated by a committee consisting of 3 independent expert pathologists, who will remain blinded. Procedures for the handling of these assessments and adjudications will be described in full in separate documents.

Pelvic examination will be performed only with the endometrial biopsy at baseline during the Screening period or the Placebo Run-in period, but at least 7 days prior to randomization, and Week 12 or early termination.

6.7.7 Routine laboratory evaluations

Blood and urine samples will be collected for routine clinical laboratory safety evaluations according to Table 1. The laboratory safety evaluations performed during the study are presented in Table 3.

Additional laboratory safety evaluations will be performed at other times, if judged to be clinically appropriate, or if the ongoing review of the data suggests a more detailed assessment of laboratory safety evaluations is required. Any changes to the scheduled times of laboratory safety tests will be agreed with the Sponsor and documented in the Trial Master File.

The Investigator will perform a clinical assessment of all laboratory data. The Investigator will record the assessment as 'normal', 'abnormal CS', or 'abnormal NCS'. Lab test abnormalities of clinical significance will be reported as AEs. Repeat lab tests or measurements will be performed for abnormal results.

Table 3 Routine Laboratory Evaluations

Hematology:	
Hemoglobin	Mean corpuscular hemoglobin
Hematocrit	Mean corpuscular hemoglobin concentration
Platelet count	Mean corpuscular volume
Red blood cell count	White blood cell count and differential
Biochemistry:	
Alkaline phosphatase	Cholesterol
Aspartate aminotransferase	Triglycerides
Alanine aminotransferase	High density lipoprotein-cholesterol
Gamma-glutamyl transpeptidase	Low density lipoprotein-cholesterol
Potassium	Protein (total)
Sodium	Albumin
Chloride	Creatine kinase
Inorganic phosphate	Creatinine
Glucose	Follicle Stimulating Hormone ¹
Urea	Estradiol ¹
Bilirubin (direct and total)	Luteinizing hormone ¹
Coagulation:	
Prothrombin time	Activated partial thromboplastin time
International normalized ratio	
Urinalysis:	
Specific gravity, pH, protein, glucose, ketones, urobilinogen, blood	
Microscopic examination ²	

¹ Screening, Week 1, and Week 12 only.

² Performed only if required, based on urinalysis results.

Blood and urine samples will be analyzed by [REDACTED] using standard methods. Procedures for the handling of samples will be described in full in a separate document.

6.8 Screening and safety-related questionnaires

6.8.1 Eight-Item Patient Health Questionnaire¹¹

The PHQ-8 is a self-rated questionnaire assessing current depressive symptoms based on 8 out of 9 criteria of the DSM-IV. See APPENDIX 7 for an example of the PHQ-8.

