2.2.5 Safety assessments

- Physical examination (including breast safety evaluation)
- Vital signs (blood pressure, pulse, and tympanic body temperature)
- ECG parameters (including cardiac intervals: heart rate, PR, QRS, QT, and QTcF)
- Clinical laboratory assessments (hematology, biochemistry, coagulation, and urinalysis)
- Reproductive hormones (luteinizing hormone [LH], follicle stimulating hormone [FSH], and estradiol [E2])
- Adverse events (AEs)
- Endometrial safety (endometrial thickness, as measured by transvaginal ultrasound, and incidence of endometrial hyperplasia, as measured by endometrial biopsy)
- Depression and anxiety symptoms as measured by 8-item Patient Health Questionnaire (PHQ-8) and 7-Item Generalized Anxiety Disorder questionnaire (GAD7), respectively

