6.8.2 Generalized Anxiety Disorder-7¹²

The GAD7 is a self-rated questionnaire assessing current anxiety levels. See APPENDIX 8 for an example of the GAD7.

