8.8 Adverse events associated with endometrial safety assessments

A transvaginal ultrasound and endometrial biopsy will be performed for subjects with a uterus. These procedures will be performed to assess endometrial safety (endometrial thickness, as measured by transvaginal ultrasound, and incidence of endometrial hyperplasia, as measured by endometrial biopsy). The scans by ultrasound will be processed and assessed centrally. Biopsy samples will be processed and assessed by central laboratories. Biopsy results will be adjudicated by a committee consisting of 3 independent expert pathologists.

The Investigator will perform an overall evaluation of the transvaginal ultrasound results and endometrial biopsy report. The Investigator will exercise medical judgment in deciding whether abnormal results are clinically significant. Abnormalities which are judged by the Investigator to be clinically significant will be recorded as AEs.

If a subject has an abnormal endometrial stripe of ≥ 5 mm thickness as measured by transvaginal ultrasound performed at Week 12 or early termination, independent of the results of endometrial biopsy, the Investigator will be informed and advised to refer subject to a gynecologist for further management. Further management and the decision to conduct a hysteroscopy and dilatation/curettage will be deferred to the physician's opinion and the subject's acceptance.

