#### **2.4.9 Depression and Anxiety**

Depression as measured by 8-Item Patient Health Questionnaire (PHQ-8). The total scores of PHQ-8 will be used as the safety endpoint.

Anxiety as measured by the 7-item Generalized Anxiety Disorder questionnaire (GAD7). The total scores of GAD7 will be used as the safety endpoint.

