### 7.10.8 Other Safety Assessments

Total score of PHQ-8 and total score of GAD7 will be summarized descriptively in tables by treatment and scheduled visit. (Table 14.3.8, Table 14.3.9) The data listings will be generated.

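### PHQ-8 and GAD7 scores have no stated link to investigator review or AE recording and are tabulated only as totals by visit, so marked worsening in a few women could go unseen in the by-arm safety tables

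*Protocol*

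**What the plan says.** Protocol 2.2.5 lists among the safety assessments "Depression and anxiety symptoms as measured by 8-item Patient Health Questionnaire (PHQ-8) and 7-Item Generalized Anxiety Disorder questionnaire (GAD7), respectively". Protocol 5.2.2 and 5.2.3.1 to 5.2.3.5 schedule both scales at Visits 2 to 7, so each woman should have pre-dose scores and repeated scores on treatment.

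The procedure text in Protocol 6.8 is one descriptive sentence per scale, plus a pointer to an appendix: "The PHQ-8 is a self-rated questionnaire assessing current depressive symptoms based on 8 out of 9 criteria of the DSM-IV" and "The GAD7 is a self-rated questionnaire assessing current anxiety levels". The other safety assessments are handled differently. For the ECG, Protocol 6.7.4 has the investigator grade the result and then says "Abnormalities of clinical significance will be reported as AEs"; Protocol 6.7.3 says the same for vital signs. For laboratory results, Protocol 6.7.7 says "Lab test abnormalities of clinical significance will be reported as AEs". For endometrial results, Protocol 8.8 says "Abnormalities which are judged by the Investigator to be clinically significant will be recorded as AEs".

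SAP 2.4.9 fixes the summary measure: "The total scores of PHQ-8 will be used as the safety endpoint", with matching wording for GAD7. SAP 7.10.8 gives the whole analysis: "Total score of PHQ-8 and total score of GAD7 will be summarized descriptively in tables by treatment and scheduled visit", followed by data listings. SAP 7.10 says the safety statistics include the minimum and maximum.

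**The concern.** Two things are missing, and they compound each other. In the protocol, nothing requires anyone at the site to look at a self-rated score, decide whether a rise matters, or record it. In the SAP, the tables describe the distribution of scores at each visit but do not follow a woman from her own baseline.

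A mood effect confined to a minority barely moves a visit mean. If the rise is also not recognised as an AE, it does not reach the TEAE tables. Safety and tolerability are a secondary objective of this dose-selection study, and Protocol 3.2 says its results will inform whether a Phase III study is warranted. A table that cannot count how many women worsened on each dose gives little help on that question for depression and anxiety.

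**Working it through.** The plan states no figure for this point, so there is none to reproduce. The check compares the text and adds an illustration.

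**1. Route from a result to an AE**

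| Assessment | Investigator evaluation and AE rule stated? |
|---|---|
| Vital signs (Protocol 6.7.3) | Yes |
| ECG (6.7.4) | Yes |
| Laboratory (6.7.7) | Yes |
| Endometrial (8.8) | Yes |
| PHQ-8, GAD7 (6.8.1, 6.8.2) | No |

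The heading of Protocol 8.5 extends to other abnormal assessments, but its only subsection concerns laboratory abnormalities. Its follow-up rule applies to results graded abnormal and clinically significant, a grade that the protocol never assigns to the questionnaires.

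**2. Tabulation**

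| Measure | Planned beyond values by visit |
|---|---|
| Laboratory (SAP 7.10.2) | Change from baseline, threshold counts |
| ECG (7.10.4) | Change from baseline, threshold counts, shift tables |
| ISI (7.9.1.4) | Change from baseline, category table |
| PSQI (7.9.3) | Change from baseline, category table |
| PHQ-8, GAD7 (7.10.8) | None, apart from listings |

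SAP 5.4.5 defines change from baseline in general, but 7.10.8 does not call for it. SAP 3.4 says nothing beyond the SAP is planned.

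**3. Which scores reach the by-visit tables**

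SAP 5.4.6 leaves unscheduled visits out of by-visit tables. Where a Table 5 window holds several visits, it keeps only the one closest to the nominal day. Example: a woman attends on Day 15, worsens, and has her early-termination visit on Day 20. Both days fall in the Week 2 window (Days 7 to 21, nominal Day 15). Day 15 is kept. The Day 20 score leaves the table, and the printed maximum with it.

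**4. Illustration of size**

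Input from the documents: 91 women per arm (Protocol 4.1). Assumed: k women rise by 10 points, nobody else changes, and the SD of the total score is 3 to 5.

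- Shift in arm mean = k × 10 / 91. For k = 1, 3 and 5 this is 0.11, 0.33 and 0.55 points.
- SE of a between-arm difference = SD × √(2/91) = 0.44, 0.59 and 0.74 for SD 3, 4 and 5.
- For k = 5, the ratio is 0.55 / 0.44, 0.55 / 0.59 and 0.55 / 0.74. From unrounded values this is 1.24, 0.93 and 0.74 standard errors.
- Counted by woman: 5/91 = 5.5% against 0/91. Fisher's exact two-sided p = 0.059, given only as a gauge because the safety analysis is descriptive.

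**5. The maximum as a backstop**

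A simulation assumed totals from 0 to 24, gamma baselines with mean/SD from 2/2.5 to 5/5, and within-woman noise with SD 2. None of these values is in the documents. With three of 91 women rising by 10 points, the arm maximum rose 3 or more points above its baseline value in about 10% to 43% of simulated arms. Noise alone produced this in 5% to 14%. The maximum carries some signal, but a weak one: it cannot tell a woman who worsened from one who entered with a high score.

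**The case against.** The case against has real force on several counts.

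- **An AE route exists.** Protocol 8.1 defines an AE broadly enough to cover new or worse mood symptoms. Protocol 8 and 8.6 require the investigator to ask about AEs at every visit. A recognised mood event would enter the TEAE tables. This stands. What is absent is a link from the score to that process, and the questioning is meant to be open and unprompted.
- **The tables are not blind.** The maximum is printed and individual scores are listed. This also stands, so a reader who infers that worsening is bound to be missed goes too far. The listings, however, give no count by arm.
- **Withdrawing women are not simply lost.** Protocol 5.2.3.5 collects both scales at early termination, and the Table 5 windows are wide, so many such scores will be tabulated. The loss is limited to unscheduled scores, early-termination scores displaced by a visit closer to the nominal day, and those outside every window.
- **The contrast is not universal.** Vital signs (SAP 7.10.3) have no stated change from baseline either. The tabulation contrast is therefore with laboratory, ECG, ISI and PSQI, the last two being efficacy measures.
- **The example is favourable.** A zero comparator and no change in any other woman are assumptions. Ordinary fluctuation would produce some rises in every arm.

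A reader might also infer that the drug acts centrally, or that the DMC would not see a mood signal. The supplied text supports neither. The Introduction places the target on primary afferent neurons and reports no mood signal. The DMC charter was not supplied, and SAP 3.2.1 and 3.2.2 are redacted.

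**Conclusion.** The point holds as a gap in planning. It is not a contradiction, and it invalidates no analysis. Two named safety measures have no stated step from score to investigator review to AE record, and their tables give only visit totals. Marked worsening in a few women could go unseen in the by-arm tables, though the maximum, the listings or a recognised AE might still reveal it.

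The size, on assumed values, is a shift of about half a point in the arm mean when five of 91 women rise by 10 points. The textual finding needs none of those assumptions. It does carry one limit: the SAP list of tables and the questionnaire appendices are not in the supplied text and some AE bullets are redacted, so table titles and scoring could not be checked. The improvement is cheap and worth making.

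**What to change.** **SAP 7.10.8.** Add change from baseline for both totals. Add a by-arm shift table, or a number and percent of women, from baseline to the worst post-baseline total. State that the worst value includes early-termination and unscheduled scores, whatever the SAP 5.4.6 rule does for the by-visit tables. The sponsor should fix the categories or cut-off in the SAP before unblinding; the documents give none.

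**Protocol 6.8.** Add the kind of sentence already used for the other safety assessments: the investigator reviews the PHQ-8 and GAD7 totals, and clinically significant worsening is recorded as an AE.

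**Cost.** Two extra tables from data already collected, one protocol sentence, and slightly more site review and AE records. No dose or treatment rule changes.
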